7.2.6 Observation period

The observation period will be a period up to 28 days after vaccination with Prevenar 13 (The day of vaccination will be defined as Day 0).

The investigator should evaluate AEs on or after Day 28 from the date of vaccination, by defining the day when the vaccinee first visits the hospital as the end day of observation. If the vaccinee does not visit the hospital, the investigator should make an inquiry to the vaccinee by phone and assess AEs. For the timing of confirmation by phone, see Table 2.

If the observation period does not meet the requirement of up to Day 28 after vaccination despite the use of the abovementioned method, and confirmation by phone cannot be made,

AEs should be evaluated with the period up to the date on which the investigator was able to confirm the information of the vaccinee for the last time regarded as the observation period.

In addition, the investigator should distribute the “Health Survey Diary for Pneumococcal Vaccine” to request vaccinees to record the results of observation during a period from the date of vaccination to Day 13 (The day of vaccination will be defined as Day 0). The diary should be retrieved at hospital visits on or after Day 13, and the investigator should interview the vaccinees to collect AEs.

Table 1. Method and timing of AE evaluation

Standard AE evaluation (at a visit)	AEs will be evaluated on or after Day 28 from the vaccination, whenever the vaccinee first visits the hospital.
Timing of AE evaluation by phone	Information on a vaccinee will be confirmed by phone if the vaccinee does not make a visit after the abovementioned period.
In the case where the observation period does not meet the requirement of 28 days after vaccination	If the observation period does not meet the requirement of up to Day 28 after the vaccination despite the use of the abovementioned method, and confirmation by phone cannot be made, AEs will be evaluated with the period up to the date on which the investigator was able to confirm the information of the vaccinee for the last time regarded as the observation period.

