7.3.5 End date of observation and discontinuation record

The investigator should enter Day 28 from the vaccination or any day after Day 28 (The day of vaccination will be defined as Day 0), whenever the vaccinee first visits the hospital (the date on which the investigator was able to confirm the information of the vaccinee), as the end date of observation. If the end day of observation does not meet the requirement of up to Day 28 from vaccination, the reason for discontinuation should be input.

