7.7 Data Analyses

1) Safety analysis set

The safety analysis set will include persons who meet the registration criteria for vaccinees and whose safety data are obtained after vaccination with Prevenar 13.

2) Method of safety analysis

The incidence (the number of vaccinees with adverse reactions/the number of vaccinees in the safety analysis set) of adverse reactions (vaccination-related AEs) will be the primary analysis endpoint, which will be tabulated. In addition, the incidence of adverse reactions will be tabulated by variable of vaccinee background, etc. to examine factors affecting the onset of adverse reactions.

The details of analysis methods should be as specified in a separately prepared statistical analysis plan.

The detailed methods for statistical analyses of data collected in the investigation will be presented in the statistical analysis plan for the investigation which will be retained by Pfizer. In the statistical analysis plan, the plan summarized in the protocol may be changed, but the definition of the primary endpoint and/or important changes in its analysis will be reflected in a protocol revision.

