5. ANALYSIS POPULATION

5.1. Safety Analysis Population

Safety analysis population includes eligible subjects who receive Prevenar13 vaccination and have available safety information. However, subjects are to be excluded if any of the following apply:

- a. CRF could not be collected at all (indicated in the report as “CRF not collected”).

- b. There was a breach or incompleteness of contract (indicated in the report as “breach or incompleteness of contract”).
- c. There was a breach of registration (indicated in the report as “breach of registration”).
- d. There was no report on administration of the vaccine to be surveyed (indicated in the report as “no information on administration”).
- e. There was no report on adverse event information (indicated in the report as “no adverse event information”).

For details on each criterion, “Guidance on criteria for inclusion or exclusion of analysis population and data handling in drug use results survey” is to be followed.

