8.2.3. Safety Analysis

8.2.3.1. Adverse Reaction

- **All adverse reaction**

Number of vaccinees experiencing adverse reactions and its proportion are to be calculated. Number of vaccinees experiencing adverse reactions and its proportion are also to be calculated by SOC and PT.

Number of adverse reactions is to be calculated. However, the same adverse reaction which occurred more than once in the same vaccinee is to be calculated as 1 adverse reaction.

- **Serious adverse reaction**

Number of vaccinees experiencing serious adverse reactions and its proportion are to be calculated by SOC and PT.

- **Details of adverse reaction**

Number of vaccinees experiencing adverse reactions and its proportion are to be calculated by SOC and PT for the following data:

- Seriousness [serious, non-serious];
- Expected/unexpected [expected, unexpected];
- Corrective treatment [yes, no];
- Outcome [not recovered, recovered with sequelae, recovering, resolved/recovered, unknown];
- Severity [mild, moderate, severe].

If the same adverse reaction (the same PT) occurred more than once in the same vaccinee, number of vaccinees experiencing the adverse reactions is to be calculated as follows:

- Seriousness: Serious if both serious and non-serious reactions occurred;
- Expected/unexpected: Unexpected if both expected and unexpected reactions occurred;
- Number of days to onset: Number of days to onset of the first reaction;
- Corrective treatment: Yes if vaccinees experienced both reactions requiring and not requiring treatment;
- Outcome: Outcome of the reaction lastly occurred in the vaccinee;

- **Severity:** If the vaccinee experienced reactions with more than one severity, select one in the following order of priority: severe, moderate and mild.

- **Timing of onset of adverse reaction**

Number of vaccinees experiencing adverse reactions and its proportion are to be calculated by timing of initial onset [Day 0, Day 1, Day 2, Day 3, Day 4, Day 5, Day 6, Days 7-27, on or after Day 28] by SOC and PT. Proportion of vaccinees experiencing adverse reactions is to be calculated as the proportion to total number of vaccinees included in the safety analysis population for all the timing of onset.

- **Occurrence of adverse reactions by inclusion of/exclusion from safety analysis population**

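### Onset-bin proportions use the whole safety population although observation length varies, so the Days 7-27 proportion and the adverse-event incidences can be understated as risks

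*SAP*

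**What the plan says.** **Observation length.** Protocol 7.2.6 plans observation from Day 0 to Day 28. It ends at the first visit on or after Day 28, with a phone inquiry if there is no visit. If neither reaches Day 28, "AEs should be evaluated with the period up to the date on which the investigator was able to confirm the information of the vaccinee"; the shorter span, ending at the final confirmed contact, becomes the observation period. No latest date is set for the closing visit. Protocol 7.3.5 has the end date entered on the CRF and adds: "If the end day of observation does not meet the requirement of up to Day 28 from vaccination, the reason for discontinuation should be input".

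**Who is analysed.** SAP 5.1: "Safety analysis population includes eligible subjects who receive Prevenar13 vaccination and have available safety information". No minimum follow-up is required. Exclusion (e) removes only vaccinees for whom "There was no report on adverse event information".

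**Denominators.** Protocol 7.7 defines the primary incidence as "the number of vaccinees with adverse reactions/the number of vaccinees in the safety analysis set". The timing table in SAP 8.2.3.1 uses single days up to Day 5 and then "Day 6, Days 7-27, on or after Day 28", each proportion being "calculated as the proportion to total number of vaccinees included in the safety analysis population for all the timing of onset".

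**What is not there.** SAP 7 (missing data), 8.1.3 (binary data), 8.2.3.2 (adverse events) and 8.2.3.3 (subgroups) contain no at-risk count, person-time rate, censoring rule or completer analysis. SAP 8.2.1 gives an overall count of vaccinees who completed the survey, and a discontinuation count worded in terms of vaccination rather than observation. SAP 9 names completion of observation as a listing item only for subjects ineligible for vaccination.

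**The concern.** A vaccinee last confirmed event-free on Day 2 stays in the safety population and adds one to the denominator of every later bin, with no chance of adding to the numerator. The proportion for a late bin is then a correct share of all first onsets across the population, but it is not the risk among people who were watched during those days. A reader of a safety table is likely to take it as the latter.

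The same applies to any incidence read as a 28-day risk. It matters least for events that cluster soon after vaccination. It matters more for late-onset reactions and for all-cause and serious adverse events, which need not cluster early. If early stopping were more common in one subgroup of SAP 5.4 than in another, the risk ratios of SAP 8.2.3.3 would also be affected, and the plan has no table in which this could be seen.

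**Working it through.** **1. The plan's own rates (Protocol 7.5.2).** 13/333 = 3.90% and 9/136 = 6.62%, as stated (3.9%, 6.6%). Pooled: 22/469 = 4.69%. These are the only investigator-reported adverse-reaction rates given for about one month. The target of 600 is set by analogy with the earlier studies, so there is no precision formula to reproduce.

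**2. Assumed inputs.** The documents give neither of the following:
- d, the share of the safety population whose observation stops early: taken as 2% to 20%.
- s, the share of events that would start after the stop: taken as 5% to 25% for reactions.

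The safety population is taken as all 600, and stopping as unrelated to later events.

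**3. Days 7-27 bin.** If the stoppers all left before Day 7 and the risk among those observed is q, the table shows q(1 - d). The relative understatement is d. With six cases as an illustration:

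| d | Observed at Day 7 | Fixed denominator | At-risk denominator |
|---|---|---|---|
| 2% | 588 | 6/600 = 1.00% | 6/588 = 1.02% |
| 5% | 570 | 1.00% | 6/570 = 1.05% |
| 10% | 540 | 1.00% | 6/540 = 1.11% |
| 20% | 480 | 1.00% | 6/480 = 1.25% |

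The exact 95% interval for 6/600 is 0.37% to 2.16%, so each shift lies well inside sampling error.

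**4. All-cause or serious events.** The understatement of a Day 0 to Day 28 incidence is d × s. If onset were even over the 29 days and stoppers were last confirmed on Day 13 (14 days observed), s = 15/29 = 51.7%. Then d = 2% gives 1.0%, 5% gives 2.6%, 15% gives 7.8% and 20% gives 10.3%, all relative. With s = 25% the range for d = 2% to 20% is 0.5% to 5.0%.

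**5. Primary adverse-reaction incidence.** The reported value is p(1 - d × s), with p = 4.69%:

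| d | s | Reported | Loss (points) |
|---|---|---|---|
| 2% | 5% | 4.69% | 0.005 |
| 5% | 10% | 4.67% | 0.02 |
| 10% | 25% | 4.57% | 0.12 |
| 20% | 25% | 4.46% | 0.23 |
| 20% | 100% (extreme) | 3.75% | 0.94 |

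For comparison, 28/600 has an exact 95% interval of 3.1% to 6.7%, a half-width of about 1.8 points.

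**6. The opposite effect.** The numerator has no Day 28 cut-off. Each vaccinee counted only for a reaction starting after Day 28 adds 1/600 = 0.17 points. Two of them (0.33 points) would outweigh the 0.23-point loss above.

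**7. Subgroup risk ratios.** With equal d and s in both groups, the factor (1 - d × s) cancels. With d = 20% in one group, 5% in the other and s = 25% in both, the ratio is multiplied by 0.95/0.9875 = 0.962, about 4% too low. Nothing in the documents says that stopping differs.

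**The case against.** A reader might infer that the 28-day and late-onset incidences **are** understated. The documents do not support that. The bias needs early stoppers who would have had later events, and no early-stop rate is given. The plan also works against early loss: truncation applies only when both the visit and the phone inquiry fail, vaccinees without adverse-event information are excluded, and anyone returning the diary at a visit on or after Day 13 has been observed at least that long. A loss of 10% before Day 7 would mean 60 vaccinees with some safety data and no contact afterwards, which may well be pessimistic. Even onset is also doubtful for all adverse events together, since these include vaccine reactions; it suits serious or unrelated events better.

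The crude incidence is a defensible choice. Protocol 7.7 defines it explicitly, it has the same form as 13/333 and 9/136, and the survey is descriptive with no decision rule. The fixed denominator is stated openly and makes the bins a breakdown of first onsets. Kaplan-Meier is not free of assumptions either, because a last contact may itself have been prompted by an event.

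Most of this stands. It rules out replacing the primary estimate and any claim of a demonstrated bias. It does not remove the gap: observation length varies in both directions, the end date is recorded, and no planned safety analysis uses it. The overall completion count in SAP 8.2.1 is not broken down by day or subgroup. The phone inquiry has no deadline, and Protocol 7.2.6 refers for its timing to Table 2, which lists investigation items.

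**Conclusion.** The point holds in limited form. Under the stated rule, unobserved vaccinees count as reaction-free, so the Days 7-27 proportion and the all-cause and serious adverse-event incidences can be understated when read as risks. For a bin that early stoppers never entered, the relative understatement equals the early-stop share, here an assumed 2% to 20%. This rests on stopping being unrelated to later events.

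For the primary adverse-reaction incidence, the loss is about 0.005 to 0.23 points over the main assumed range, against a confidence-interval half-width of about 1.8 points. The net direction is uncertain because onsets after Day 28 are counted too. The bin for Day 28 and later has no defined risk window, so it cannot be called understated at all. Distortion of the subgroup risk ratios is possible but not shown.

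The change is worth making because it needs no new data and lets readers judge the late-period figures.

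**What to change.** - Keep the crude incidence as the protocol-defined primary, and keep the fixed-denominator timing table, labelled as a breakdown of first onsets.
- In that table, add for each bin the number still under observation at its start, from the recorded end date, and the proportion on that denominator.
- Show Day 28 separately from later onsets. Give later onsets as counts only.
- As a sensitivity analysis, add a Kaplan-Meier cumulative incidence to Day 28, censored at the end of observation, for adverse reactions, all adverse events and serious adverse events. State that it assumes uninformative censoring. It also deals with vaccinees who leave part-way through the wide Days 7-27 bin, which a start-of-bin count does not.
- Report the number observed to Day 28 overall and by SAP 5.4 subgroup, so that differential stopping can be checked.

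Cost: SAP wording and a few extra table columns, using a date already on the CRF. Late-period proportions will look slightly higher.

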8.2.3.2. Adverse Event

- **All adverse events**

Number of vaccinees experiencing adverse events and its proportion are to be calculated by SOC and PT.

- **Adverse events by seriousness**

Number of vaccinees experiencing serious adverse events and its proportion are to be calculated by SOC and PT. Also, number of vaccinees experiencing non-serious adverse events and its proportion are to be calculated by SOC and PT.

8.2.3.3. Subgroup Analysis

Number of vaccinees experiencing at least one adverse reaction and its proportion are to be calculated by subgroups as defined in [Section 5.4](#) (excluding subjects ineligible for vaccination). To assess the association between vaccinee characteristics and occurrence of adverse reactions, risk ratio and its 95% confidence interval are to be calculated as described in [Section 8.1.3](#).

To evaluate the safety in specific populations of vaccinees in detail, analyses are to be performed in the following subgroups.

- **Vaccinees with hepatic dysfunction, renal dysfunction and simultaneous vaccination with other vaccine**

Number of vaccinees experiencing adverse reactions and its proportion are to be calculated by SOC and PT in each subgroup.

- **Vaccinees with immunocompromised complication**

Number of vaccinees experiencing adverse reactions, local and systemic reactions and adverse events with its proportion are to be calculated by SOC and PT.

- **Vaccinees with prior vaccination of polyvalent pneumococcal polysaccharide vaccines**

Number of vaccinees experiencing adverse reactions, local and systemic reactions and adverse events with its proportion are to be calculated by SOC and PT by prior vaccination of polyvalent pneumococcal polysaccharide vaccines [1 year ago from the day before Prevenar13 vaccination, 1-5 years ago, more than 5 year ago, unknown date].

- **Vaccinees with immunocompromised complication and prior vaccination of polyvalent pneumococcal polysaccharide vaccines**

Number of vaccinees experiencing adverse reactions, local and systemic reactions with its proportion are to be calculated by SOC and PT by prior vaccination of polyvalent pneumococcal polysaccharide vaccines [1 year ago from the day before Prevenar13 vaccination, 1-5 years ago, more than 5 year ago, unknown date].

- **Subjects ineligible for vaccination**

Reports described below are to be prepared for subjects ineligible for vaccination (See [Section 5.4](#)) and used as a reference for reporting safety information of these subjects. If there are less than 10 subjects ineligible for vaccination, however, safety information of these subjects are to be reported with a listing of vaccinees and other forms, and reports described below are not to be prepared.

Number of subjects ineligible for vaccination as described in the package insert and its proportion are to be calculated. In addition, number of the following subjects ineligible for vaccination as described in the package insert which would be identifiable in this survey is to be calculated:

- Subjects with apparent pyrexia;
- Subjects with documented serious acute disease.

Number of subjects ineligible for vaccination with at least one adverse reaction is to be calculated.

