6.1. Safety Specifications

- 1) Safety in persons with immunocompromised state
- 2) Safety of concurrent vaccination with other vaccines
- 3) Safety in the elderly (adults aged 65 years or older) who received multiple vaccinations with Prevenar 13
- 4) Safety of Prevenar 13 in the elderly (adults aged 65 years or older) with a history of immunization with polyvalent pneumococcal capsular polysaccharide vaccines

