7.3.3 Concomitant therapies

Information on vaccines falling into the following should be entered:

- 1) Vaccines concurrently administered with Prevenar 13

- (1) Name of concurrently administered vaccine
 - (2) Administration site
- 2) Vaccines administered before Day 28 after vaccination with Prevenar 13 (The day of vaccination will be defined as Day 0.)
- (1) Name of vaccine
 - (2) Date of vaccination

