7.3.7 AEs

The investigator should record the below mentioned information after checking the occurrence of AEs during the AE collection period. Particularly, the vaccinees should be explained to notify local and systemic reactions, if occurred, to the investigator. If AEs are identified, the investigator should take appropriate therapeutic actions, immediately inform the sponsor, and monitor the outcome and course until symptoms resolve, as a rule. If the sponsor determines it necessary in vaccinees with serious adverse reactions, adverse reactions such as local and systemic reactions in the investigation, adverse reactions not specified in the package insert, etc., a detailed investigation should be separately performed.

- (1) Whether or not AEs occurred
- (2) AE term
- (3) Date of onset
- (4) Severity
- (5) Therapeutic action taken or not taken (if taken, its detail)
- (6) Seriousness
- (7) Outcome
- (8) Causal relationship with Prevenar 13

[Assessment of severity]

The investigator should record the maximum severity during the period from the onset of the AE to the confirmation of its outcome using mild, moderate, or severe (for pyrexia, mild, moderate, severe or possibly life-threatening). The severity will be defined as follows (Table 3):

Table 3 Definition of severity

	Absent	Mild	Moderate	Severity	Possibly life-threatening
Injection site erythema and swelling	< 2.5 cm	≥ 2.5 cm, ≤ 5.0 cm	> 5.0 cm, ≤ 10.0 cm	> 10.0 cm	-
Pyrexia	< 37.5°C	≥ 37.5°C, ≤ 38.4°C	≥ 38.5°C, ≤ 38.9°C	≥ 39.0°C, ≤ 40.0°C	> 40.0°C
Other AEs	-	Not interfering with the normal function of the vaccinee	Interfering with the normal function of the vaccinee to some degree	Significantly interfering with the normal function of the vaccinee	-

[If an AE of pyrexia occurs, the following information should be additionally entered:]

- (1) Date of measurement
- (2) Body temperature

Be sure to record the maximum body temperature during the period from the onset of pyrexia to its resolution.

[In the case of AEs related to laboratory tests, etc. and abnormal changes in test values, the following should be additionally entered:]

- (1) Name of test
- (2) Site reference value
- (3) Unit
- (4) Date of measurement
- (5) Results

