9.3 Assessment of the Causal Relationship

The investigator will be required to assess and record the causal relationship. Furthermore, he/she shall obtain adequate information for assessing the causal relationship for each AE.

For AEs related to Prevenar 13, the investigator will be required to carry out a follow-up investigation until the event or its associated sequela resolves, or becomes stable to the extent it can be accepted by the investigator, and Pfizer agrees with the judgement.

The assessment of the causal relationship by the investigator should be made based on whether or not Prevenar 13 may have reasonably caused the AE or be of its cause. When the final assessment of the causal relationship by the investigator is “unknown” and whether or not Prevenar 13 has caused the event cannot be determined, the safety event shall be reported within 24 hours.

When the investigator cannot identify the cause of the event but judges that Prevenar 13 has not caused the event, such a fact should be specified in the CRF and NIS AE Report Form.

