5.4. Subgroup

Safety analysis by subgroup is to be performed for the following subject characteristics:

- Gender [male, female] (reference population: male).
- Hepatic dysfunction [no, yes] (reference population: no): Hepatic dysfunction is identified in accordance with separately prescribed “procedure for extracting hepatic or renal dysfunction”.
- Renal dysfunction [no, yes] (reference population: no): Renal dysfunction is identified in accordance with separately prescribed “procedure for extracting hepatic or renal dysfunction”.
- Age at the time of vaccination [≥ 65 , < 70 ; ≥ 70 , < 75 ; ≥ 75 , < 80 ; ≥ 80 , < 85 ; ≥ 85] (reference population: ≥ 65 , < 70).

Safety analysis by subgroup is to be performed for the following other characteristics:

- Immunocompromised complication [no, yes] (reference population: no): Complication is identified in accordance with separately prescribed “definition of ‘immunocompromised’ in P13 adults”.
- Simultaneous vaccination with other vaccine [no, yes] (reference population: no).
- More than once Prevenar13 vaccination [once, more than once] (reference population: once).

- Prior vaccination of polyvalent pneumococcal polysaccharide vaccines [no, 1 year ago from the day before Prevenar13 vaccination, 1-5 years ago, more than 5 year ago, unknown date] (reference population: no).
- Subjects ineligible for vaccination: Subject population ineligible for vaccination as described in the package insert. Criteria for subjects ineligible for vaccination is based on separately prescribed “procedure for extracting subjects ineligible for vaccination”. Reference population is not used since there is no category within the subgroup.

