6. ENDPOINTS AND COVARIATES

6.1. Safety Endpoints

- Adverse reaction: Adverse event whose causal relationship is confirmed by investigator or sponsor.
- Adverse event: Adverse event regardless of causal relationship.
- Priority survey items: No priority survey items in this survey.

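### Concurrent vaccination is compared only through events attributed to Prevenar 13, so its risk ratio may be biased downward; an all-cause comparison should stand beside it

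*SAP*

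**What the plan says.** Protocol 6.1 names four safety specifications. The second is "Safety of concurrent vaccination with other vaccines". SAP 5.4 makes simultaneous vaccination a yes/no subgroup with no as the reference.

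The SAP plans three safety outputs split by this factor:

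- a risk ratio with 95% CI for at least one adverse reaction (8.2.3.3);
- a SOC/PT table, where the instruction is "Number of vaccinees experiencing adverse reactions and its proportion are to be calculated by SOC and PT in each subgroup" (8.2.3.3);
- a pyrexia table (8.2.3.1).

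SAP 6.1 defines an adverse reaction as "Adverse event whose causal relationship is confirmed by investigator or sponsor". That line does not name the product, but the only causality item listed in Protocol 7.3.7 is "Causal relationship with Prevenar 13". Protocol 9.3 tells the investigator to judge "whether or not Prevenar 13 may have reasonably caused the AE or be of its cause".

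For the immunocompromised subgroup, SAP 8.2.3.3 asks for more: "Number of vaccinees experiencing adverse reactions, local and systemic reactions and adverse events with its proportion are to be calculated by SOC and PT". The group with prior polysaccharide vaccination gets the same set, split by time since that vaccination.

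**The concern.** The specification asks whether giving Prevenar 13 with another vaccine is safe. A second vaccine given on the same day offers an alternative explanation for any event that follows. If the investigator and the sponsor both assign an event entirely to that vaccine, it is not an adverse reaction under the SAP and leaves the numerator. A person given Prevenar 13 alone has no co-administered vaccine to which an event could be assigned. The outcome filter can therefore depend on the exposure being compared.

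A risk ratio near 1 could then mean either that concurrent vaccination adds little or that some of its reactions were credited to the other product. The planned tables cannot separate these readings, because none that is split by simultaneous vaccination counts events regardless of causality.

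**Working it through.** **1. The plan's own figures.** The sample size of 600 was set to match the scale of the earlier Japanese studies. It has no power or precision formula to reproduce. The rates quoted with it check: 13/333 = 3.9%, 9/136 = 6.6%, and 333 + 136 = 469. Pooled, 22/469 = 4.69%.

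**2. Which numerator each output uses.**

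| Output | Split by simultaneous vaccination? | Numerator |
|---|---|---|
| Risk ratio, SAP 8.2.3.3 | Yes | Adverse reactions |
| SOC/PT table, SAP 8.2.3.3 | Yes | Adverse reactions |
| Pyrexia, SAP 8.2.3.1 | Yes | Adverse reactions (by definition, 10.2.3) |
| Local and systemic reactions, SAP 8.2.3.1 | No | Adverse reactions (by definition, 10.2.1 and 10.2.2) |
| All adverse events, SAP 8.2.3.2 | No | All causes |
| All adverse events, immunocompromised and prior-polysaccharide groups, SAP 8.2.3.3 | No | All causes |

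Every output split by this factor passes through the causality filter. The all-cause tables are not split by it.

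**3. Effect on the risk ratio.** Let p1 be the true risk of at least one reaction, to either vaccine, in the co-vaccinated group. Let p0 be the risk with Prevenar 13 alone. Let m be the share of co-vaccinated persons with a reaction whose every reaction is attributed only to the other vaccine. Then

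observed ratio = p1 × (1 − m) / p0 = true ratio × (1 − m).

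The documents do not give m. For an assumed true ratio of 2.0:

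- m = 0: 2.0 × 1.00 = 2.0
- m = 10%: 2.0 × 0.90 = 1.8
- m = 25%: 2.0 × 0.75 = 1.5
- m = 50%: 2.0 × 0.50 = 1.0

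**4. What that does to a small subgroup.** The number of co-vaccinated persons is not given either. Take 60 of 600 as an assumption, with p0 = 4.69%. Expected co-vaccinated persons with a reaction at a true ratio of 2.0 are 60 × 2.0 × 0.0469 = 5.6. At m = 25% this is 5.6 × 0.75 = 4.2. Power at a nominal two-sided 0.05 falls from 38% to 16%. With 30 co-vaccinated it falls from 27% to 12%, and with 180 from 58% to 23%. SAP 4.1 sets no significance level, so power serves here only as a yardstick. These figures leave out the background events that an all-cause count would add to both groups.

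**The case against.** The strongest reply is that the causality rule is inclusive. Under Protocol 9.3 an event counts if Prevenar 13 may reasonably have contributed, and SAP 6.1 accepts attribution by either the investigator or the sponsor. An ambiguous systemic event on the day of vaccination may well stay in. This stands. A reader might infer that same-day events, or reactions at the other injection site, will drop out as a matter of course. The documents do not support that: an event is lost only if Prevenar 13 is rejected as a contributor. If other-site reactions are recorded as related to Prevenar 13, they are counted.

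The unit also limits the loss. The risk ratio counts persons, so one reaction linked to Prevenar 13 keeps a person in. Losing a quarter of reactions is not losing a quarter of persons. For someone with two reactions, each lost independently with an assumed probability of 25%, the chance of losing the person is 0.25 × 0.25 = 6.25%.

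The information itself is not lost. All adverse events are recorded (Protocol 9.1), tabulated overall (SAP 8.2.3.2) and listed by vaccinee (SAP 9), and SAP 8.2.3.4 allows further analysis. This also stands, but a listing is not a comparison, and exploratory results are reported only if judged important to interpretation.

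Finally, an all-cause ratio compares two vaccines with one. The second vaccine's own reactions can raise it with no interaction at all, and no group receives only the other vaccine. Protocol 7.9 already states the limits of having no control group. This is a sound reason not to let the all-cause ratio replace the adverse-reaction ratio. It is no reason to leave it out.

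**Conclusion.** The concern holds as a gap in the planned comparison. Specification 2 is assessed only with an outcome whose filter can depend on exposure. The possible loss to a co-administered vaccine is one-sided, so any bias from it in the adverse-reaction risk ratio, read as a measure of the safety of concurrent vaccination, is downward. The ratio is multiplied by (1 − m): a true 2.0 is seen as 1.8 at m = 10% and 1.5 at m = 25%. Both values of m, the true ratio of 2.0 and the subgroup size are assumptions. The documents show that the loss can occur, not that it is large.

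Two stronger readings should be resisted. A reader might infer that a real doubling would vanish. That needs half of the co-vaccinated persons with a reaction to have every reaction assigned solely to the other vaccine, and nothing in the documents suggests so high a share. A reader might also infer that the all-cause ratio should be the main result for this specification. It cannot isolate added Prevenar 13 risk, and the protocol's primary endpoint is the incidence of adverse reactions. It belongs beside the existing ratio.

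**What to change.** In SAP 8.2.3.3, for the simultaneous-vaccination factor:

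- Tabulate adverse events regardless of causality by SOC and PT, in separate columns for vaccinees with and without simultaneous vaccination.
- Add a risk ratio with 95% CI for at least one adverse event regardless of causality, by the method in SAP 8.1.3, beside the adverse-reaction risk ratio and not in place of it.
- Where local and systemic events are shown for this comparison, select them by the term lists in SAP 10.2.1 and 10.2.2 regardless of causality. The definitions there carry the same filter, so adding those tables unchanged would not address the problem.
- State with the results that the all-cause ratio includes background events and the second vaccine's own reactions. It describes the total burden of concurrent vaccination, not an interaction or an added risk from Prevenar 13.

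The cost is a few SAP lines and the added tables and ratio. Adverse events and the "Name of concurrently administered vaccine" are already collected, so no new data field is needed. That matters because SAP version 1.1 is dated December 2016, after the planned end of the survey in October 2016.
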